3.1. Objective(s) Clearly and concisely define the primary and secondary outcomes.	3.2. Endpoint Clearly define the endpoints. (endpoints are the basis for concluding that the objective has been met).	3.3. Justification for Endpoint Briefly explain why the endpoint(s) were chosen.
Primary Histologic Outcome	% vital bone formation	% vital bone formation shows the amount of new bone formed after the procedure. The higher this % is the better the healing of the site
Secondary histologic outcomes	% residual graft material, and % "CT/other" (fibrous tissue and marrow space)	% residual graft material shows how much of the graft material remained intact. Ideally all the graft materials should turn over to vital bone % CT/other (fibrous tissue and marrow space) is the amount of tissue that is neither native bone or graft material. It may be connective tissue that will mature to osteoid and bone or marrow space that is part of the normal healing
Secondary Clinical outcomes	Change in ridge width; Change in buccal ridge height; Change in lingual ridge height	Clinical measurements show effects of procedures on dimensional changes in the alveolar ridge during healing

4. Rationale

Briefly state the reason for conducting the clinical trial.

Allografts and xenografts are commonly used in ridge preservation procedures. Demineralized freeze-dried bone allografts (DFDBA) are available in particulate and fibers forms. Newer products on the market combine xenografts and DFDBA, but there are little data on histologic healing. Our group is known for this type of research, and we wish to determine if DFDBA fibers result in similar or different histologic outcomes than DFDBA particulate, and whether bovine-derived xenograft combined with DFDBA fibers result in similar or different histologic outcomes than xenograft combined with DFDBA particulate. Finally, we will be able to assess histologic outcomes when particulate DFDBA is used alone versus when it is combined with xenograft and when DFDBA in fiber form is used alone versus when it is combined with xenograft.

5. Study Design

5.1. Number of Groups/Arms	4	Group name(s)	
 1. Group 1: DFDBA particulate at 125-850 micron size (Vallos) 2. Group 2: Xenograft (Bio-Oss) combined with DFDBA particulate at 125-850 micron size (Vallomix) 3. Group 3: DFDBA fibers (Vallos-F)
-----------------------------------	---	----------------------	---

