5.2. Overall Design Select all applicable						
	Randomization					
	Group-Sequential					
	Parallel Design					
	Superiority					
Device		Pilot				
		Pivotal				
			Post-Approval			
Drug/Biologic	Phase 1	Phase 1/2	Phase 2	Phase 2/3	Phase 3	Phase 4
Dose escalation	If yes, details →					
Dose ranging	If yes, details →					
Sub-studies	If yes, details →					
5.3. Other Design Details: This protocol summary is for a study entitled, " A 4-arm randomized controlled trial of wound healing following tooth extraction and ridge preservation using DFDBA alone in particulate or fiber form, and in combination with xenograft. " The primary aim of the study is to determine the amount of newly formed vital bone, residual graft material, and "connective tissue/other" 18 to 20 weeks after ridge preservation is performed using DFDBA fibers alone, DFDBA particulate alone, a combination of xenograft and DFDBA particulate, or a combination of xenograft and DFDBA fibers. The study only involves use of these FDA-approved materials in an FDA-approved manner (for ridge preservation).						
The study is a 4-arm, parallel-design, randomized, prospective clinical trial. The study is designed to examine histologic wound healing 18 to 20 weeks following ridge preservation. The study arms include: 
 1. Group 1: DFDBA particulate at 125-850 micron size (Vallos) 2. Group 2: Xenograft (Bio-Oss) combined with DFDBA particulate at 125-850 micron size (Vallomix) 3. Group 3: DFDBA fibers (Vallos-F) 4. Group 4: Xenograft (Bio-Oss) combined with DFDBA fibers (Vallomix-F) 						
The patient and the individual doing histomorphometry will be blinded as to study group allocation. The surgeon cannot be blinded in this study.						
Null hypothesis: There will be no significant between-group difference in vital bone formation after ridge preservation.						
Based on power analysis and drop-out experience from previous studies, we plan to ask our IRB for approval to enroll 30 patients in each of the 4 study groups, with a total of 120 patients for the 4 study groups combined.						

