the bony crest. Prior to tooth extraction, the clinical measurement stent will be placed and measurements of ridge width and ridge height will be taken and recorded to the nearest 0.5mm. Ridge width will be measured to the nearest 0.5mm using a ridge caliper at a point **approximately 3mm apical to the facial and lingual bony crest** through small holes created in the stent at those locations. Ridge height will be measured to the nearest 0.5mm through two holes in the occlusal aspect of the stent – one hole directly above the facial bony crest and another hole directly above the lingual bony crest. This stent will be retained for use during the subsequent implant placement surgery.

Use of the stent and subsequent measurements are for research purposes, not standard care.

Tooth extraction will be performed as atraumatically as possible. Following tooth extraction, a final determination of enrollment into the study will be conducted based on the integrity of the buccal bone wall plate at the extraction site. If the buccal plate is intact, defined as **no bony dehiscence greater than 50% of the socket depth**, the patient will remain enrolled in the study. Conversely, if the buccal plate integrity has not been maintained (bony dehiscence >50%) the patient will be exited from the study and standard care therapy will be delivered to the patient.

After extraction, the number of bony walls in each socket will be recorded along with the presence of any bony dehiscences or fenestrations. Buccal and lingual flap elevation will be minimized and will extend no more than 2-3mm beyond the bony crest on the facial and lingual surfaces. The buccal plate thickness will be measured using an Iwanson gauge positioned perpendicular to the inner wall of the extraction socket. One beak of the gauge will be placed within the extraction socket 1.0mm apical to the alveolar bone crest. The other beak will be placed on the external bone surface 1.0mm apical to the alveolar bone crest. This buccal plate thickness measurement will be recorded to the nearest 0.1 mm. Measurements taken with the Iwanson gauge are for research purposes, not standard care.

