The implant surgery will be performed (standard care) at a time point 18 to 20 weeks after tooth extraction/ridge preservation (± 2 weeks). Per standard care, after local anesthesia (and conscious sedation if requested), the patient will undergo implant placement surgery at the previously extracted tooth site and if required simultaneous guided bone regeneration (GBR) will be performed as per standard care. First, the individual subject's measuring stent and caliper will be used to determine the ridge width and ridge height at the same locations as done in the tooth extraction/grafting surgery visit and all measurements will be documented for research purposes. During the implant bed preparation, a hollow drill will be used to allow retrieval of a bone core which will be collected and stored in formalin and subsequently examined histologically and outcomes including percentages of new bone formation, residual graft and connective tissue/other will be recorded. (Drilling procedure is per standard of care, collection of normally discarded bone core for analysis is a research procedure).

During the implant placement procedure, the following data will be recorded per standard care:

- Absence/Presence of bone defect, including dehiscence or crater like defect. If present, at what site(s) (Buccal, Mesial, Lingual, Distal) and what are the respective depth and width of these defects.

- Absence/Presence of bone fenestration. If present what is the size of the fenestration in height and width.
- Bone quality according Lekholm and Zarb (1985) classification
- Was additional bone grafting needed in case of thin bone or dehiscence of threads? Yes/No

Subject participation ends at the time of implant placement. However, standard care post-operative visits will be provided after implant placement. Generally, one or two post-operative visits will be provided during the first month after implant surgery to insure adequate healing.

6. Study Population

6.1. Study Population(s) Label/Name	6.2. Identify the criteria for inclusion The criteria that every potential participant must satisfy, to qualify for study entry.	6.3. Identify the criteria for exclusion The characteristics that make an individual ineligible for study participation.

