Randomization of subjects is done through use of envelopes inside which is a piece of paper with the group to which the subject will be assigned. 30 envelopes will be prepared for each of the 4 groups. The envelopes will be sealed and shuffled. The faculty staffing the procedure will draw an envelope from the stack prior to the surgical procedure appointment. Since the outcome of the study is the histologic healing, blinding of the surgeon is not necessary.
Blinding is performed only for histomorphometric measurements. The person doing histomorphometric analysis is blinded as to study group.
10.2. Study Intervention Compliance Define how adherence to the protocol (e.g., administration of study intervention, use of device,) will be assessed, and verified (if applicable, e.g., plasma assays, electronic monitoring devices, daily diaries).
Patients will need to be present at each scheduled visit. Failure to attend visits will result in exit from the study. All providers placing study materials as part of the study intervention will be trained and provided with detailed instructions to ensure methods are consistent and in compliance with the protocol. All faculty staffing residents are familiar with the study protocol and can verify the results of the procedure and measurements taken.
10.3. Permitted Concomitant Therapy This section should be consistent with the medication restrictions in the inclusion/exclusion criteria previously listed. Describe how allowed concomitant therapy might affect the outcome (e.g., drug-drug interaction, direct effects on the study endpoints).
N/A
10.4. Rescue Medicine List all medications, treatments, and/or procedures that may be provided during the study for "rescue therapy" and relevant instructions.
N/A, no rescue medicine

11. Study Intervention Discontinuation
11.1. Discontinuation of Study Intervention Describe the criteria for discontinuing the study intervention (e.g., halting rules), including any monitoring test(s) and associated clinical decision point(s). Include reasons for temporary discontinuation of the study intervention (e.g., type and quantity of adverse events), clearly stating the length of time, if applicable, and describe the data to be collected at the time of study intervention discontinuation and approaches for restarting administration of or re-challenging with study intervention.

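### No masked reader is specified for the three secondary ridge outcomes, and the reason given for not blinding the surgeon overlooks them; the timing of the envelope draw also needs reconciling.

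*Combined protocol and SAP*

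**What the plan says.** **Blinding.** Section 10.1 gives this reason for leaving the surgeon unblinded: "Since the outcome of the study is the histologic healing, blinding of the surgeon is not necessary". It then sets the scope: "Blinding is performed only for histomorphometric measurements". Section 5.3 differs on two counts. It gives feasibility as the reason, "The surgeon cannot be blinded in this study", and it adds the patient to those who are masked: "The patient and the individual doing histomorphometry will be blinded as to study group allocation".

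**Ridge outcomes.** The endpoint table in Section 3 lists as secondary clinical outcomes "Change in ridge width; Change in buccal ridge height; Change in lingual ridge height". Section 12.1 makes ridge dimension part (b) of the null hypothesis. Section 12.4 applies the ANOVA, post-hoc and pairwise plan to both histologic and clinical parameters.

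**How they are read.** At Visit 2, before extraction, "Ridge width will be measured to the nearest 0.5mm using a ridge caliper at a point" located by the stent; heights are read through stent holes at the same resolution. At Visit 5 the same "measuring stent and caliper will be used to determine the ridge width and ridge height at the same locations", before the core is taken. Neither visit description says who measures. Section 10.2 says only that faculty supervising the residents "can verify the results of the procedure and measurements taken".

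**When the arm is known.** Section 10.1 has the supervising faculty draw the envelope before the surgical appointment. Section 5.3 (Visit 2) places randomization after extraction and socket debridement, and so after the ridge readings and the final decision on buccal-plate integrity.

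**The concern.** The Section 10.1 rationale treats histology as the only outcome. For histologic outcomes read by a blinded person it is a fair argument about assessment. It does not cover three outcomes that are read by hand in the surgical setting and then formally tested.

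A ridge outcome is a change score, so any arm-related tendency in either reading passes straight into it and cannot be told apart from an effect of the graft material. With the envelope timing in Section 10.1, the baseline reading is exposed as well as the follow-up one.

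That timing also touches the post-extraction decision to keep or exit a patient on buccal dehiscence. If the arm is known when that judgement is made, knowledge of the arm could influence who stays in each group.

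**Working it through.** The plan states no figure on this point, so the main check is to compare its sections. The arithmetic is only a sensitivity illustration.

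**Step 1: does the stated reason cover every tested outcome?**

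| Outcome | Status (Sections 3, 12.1, 12.4) | Masked reading specified? |
|---|---|---|
| % vital bone | Primary, tested | Yes (5.3, 10.1) |
| % residual graft, % CT/other | Secondary, tested | Yes (5.3, 10.1) |
| Change in ridge width, buccal height, lingual height | Secondary, null hypothesis (b), tested | No |

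The reason fails for the last row.

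**Step 2: who reads the ridge?** The text is silent. Three facts point to an unmasked reader: the readings are taken at the surgeries, blinding is confined to histomorphometry, and the only named check is by supervising faculty, the group that draws the envelope. That supports a strong inference and no more.

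**Step 3: is the arm known at baseline?** Section 5.3 gives the order readings, extraction, buccal-plate decision, debridement, randomization. Section 10.1 puts the envelope draw ahead of the appointment. It says drawn, not opened, so exposure is possible but not established. The two sections conflict as written.

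**Step 4: sensitivity illustration.** From the documents:
- 30 enrolled per group and 20% attrition (Section 12.2), giving 30 × 0.80 = 24 per group;
- two-sided 5% tests and two-sample t-tests for pairwise comparisons (Section 12.4).

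Assumed, because the documents give no value:
- SD of ridge change, 1.0 to 2.0 mm;
- differential mean shift b between two arms from reading alone, with no true difference.

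The t statistic is noncentral with df = 2 × 24 − 2 = 46 and noncentrality λ = (b/SD) × √(24/2) = 3.464 × b/SD. The rejection probability is P(|T| > 2.013).

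| Shift b | SD 1.0 | SD 1.5 | SD 2.0 |
|---|---|---|---|
| 0.25 mm | λ = 0.866, 13.6% | λ = 0.577, 8.7% | λ = 0.433, 7.1% |
| 0.50 mm | λ = 1.732, 39.6% | λ = 1.155, 20.4% | λ = 0.866, 13.6% |

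With all 30 per group the same grid runs from 7.6% to 47.8%. A mean shift of 0.1 mm with 24 per group gives 5.3% to 6.3%.

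**Step 5: which row is plausible?** Rounding a true value to the nearest 0.5 mm moves it by at most 0.25 mm. A 0.50 mm mean shift needs, for example, every patient in one arm to be read one full step off in the same direction. A 0.25 mm mean shift needs about half of them to be (0.5 × 0.5 mm). The upper row is therefore the more useful guide, and the lower row is an extreme.

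**The case against.** The case on the other side has real content.

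- **The surgeon cannot be blinded.** Section 5.3 says so, and this is a sound reason independent of Section 10.1. It stands. The gap is the absence of a masked ridge reader, not the unblinded surgeon.
- **The reader is not named.** A reader might infer that the plan has the unblinded surgical team take the ridge measurements. The documents do not say that; the descriptions of both visits are silent on it.
- **The stent standardises location.** Fixed holes limit discretion. They do not remove it, since a caliper or probe value still has to be judged.
- **The order of events is partly right already.** Visit 5 readings precede the core, and Section 5.3 randomizes after the baseline readings. Both stand, so the envelope problem is a conflict to resolve rather than proof of exposure.
- **The size is assumed.** SD and shift are not in the documents, and the 0.5 mm resolution is stated only for Visit 2. No direction of bias is shown: all grafts come from one supplier, and the rationale asks whether materials are similar or different. This stands, so the figures show sensitivity and are not a forecast.
- **Using another clinician in the room may not mask.** A supervising faculty member who drew the envelope knows the arm, or may, even without having placed the graft. This stands and shapes the fix.

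**Conclusion.** The point holds in limited form. The rationale in Section 10.1 is wrong for three planned and tested secondary outcomes, and no masking is specified for them. That the readings will be unmasked is a strong inference from the setting.

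On size: with an assumed SD of 1 to 2 mm and 24 per arm, a 0.25 mm differential mean shift would take a nominal 5% pairwise test to about 7-14%, and the extreme 0.5 mm shift to about 14-40%. A 0.1 mm shift would hardly matter (5-6%). These figures say what bias would do if present. They are not evidence that it will occur.

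A reader might infer that the main conclusion is compromised. The documents do not support that: the primary and secondary histologic outcomes are read blinded, and ridge-reading bias does not reach them. The envelope conflict is a distinct matter. If Section 10.1 is followed and the envelope is opened early, the baseline readings and the eligibility decision could both be made with the arm known. The change is worth making because it is specific and nearly free.

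**What to change.** 1. **Reconcile Section 10.1 with Section 5.3 (Visit 2) on allocation.** State that the sealed envelope is drawn and opened only after the Visit 2 ridge readings and the final buccal-plate eligibility check have been recorded.
2. **Correct the rationale in Section 10.1.** Replace it with the feasibility reason from Section 5.3, and state that this leaves the ridge outcomes open to assessor bias.
3. **Specify the Visit 5 reader.** Where a clinician already present neither placed the graft nor drew or saw the allocation, have that person take the readings on a sheet showing neither the arm nor the Visit 2 values. Record who measured and whether they knew the arm. Otherwise report the ridge outcomes as assessed unmasked and interpret them accordingly.
4. **Reconcile Sections 5.3 and 10.1 on patient blinding.** One says the patient is masked; the other limits blinding to histomorphometry.

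The cost is protocol wording, a separate recording sheet and minor scheduling. No added staff, visit or procedure is needed. Where no unaware clinician is present, the readings stay unmasked and the remedy is disclosure.

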In keeping with the protocol our study group has used numerous times before, the plan is to extract non-molar teeth and graft with the various graft materials. Each subject will provide a single non-molar tooth site for study treatment. Following approx. 18-20 weeks of healing, we will harvest a core biopsy at the time of implant placement. The implant osteotomy is prepared with a trephine drill and the core inside the trephine is placed in 10% formalin for future processing and histomorphometric analysis. The core biopsy will be evaluated for the primary histologic outcome of % vital bone formation and the secondary histologic outcomes of % residual graft material, and % "CT/other" (fibrous tissue and marrow space). We will also evaluate the following secondary clinical outcomes using a custom measuring stent for each subject: change in ridge width; change in buccal ridge height and change in lingual ridge height. During the 18 to 20-week healing period, patients will be followed as needed per standard care to evaluate healing.

A detailed visit by visit outline is provided below:

Step-by-Step Methods: All the procedures are routinely performed in the graduate periodontics clinic as part of standard care. The methodology is the same previous studies of our group HSC20130470H, HSC20150708H, HSC20170339H, HSC20170267H, HSC2019-0455H, among others.

Visit 1 - Screening examination:

If a patient presents at a consultation appointment at the graduate periodontics clinic with a non-molar tooth (incisors, canines, premolars) that needs to be extracted and replaced with a dental implant, the treating doctor will provide:

- Explanation to the patient of the purposes of the study and the planned procedures related to the study.
- Explanation to the patient of the risks, benefits and possible complications of participation in the study.
- Notification to the patient that inclusion in the study is voluntary and that they will still receive standard of care treatment if they choose not to participate, and conditional upon satisfying the inclusion and exclusion criteria.

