The socket will be thoroughly debrided, the patient will be randomized to one of the study groups (Group 1, 2, 3 or 4), and the graft material will be placed in the extraction socket to a level even with the interproximal bone height of the mesial and distal aspects of the socket. The material will be condensed into the socket gently. In all sockets, a BioGide resorbable collagen membrane will be placed over the socket and graft material to retain the material in place. The edges of the membrane will be “tucked” under the flap margins to help with membrane retention, and the flaps will be sutured. Primary closure of the flaps will not be performed, per standard care. Flaps will be stabilized with chromic gut sutures, per standard care.

Visit 3 - Post-operative visit

The post-operative visit after extraction/ridge preservation will be scheduled approximately 3 weeks (± 1 week) after the procedure. At this visit a clinic exam will be performed to evaluate healing. Any remaining sutures will be removed. If needed, an optional POT visit may be scheduled before this visit, per standard care and as determined by patient need.

Visit 4 - Pre-implantation:

Approximately 3-4 months after the extraction, the patient will be seen for pre-implant evaluation, per standard care. If needed, a cone beam computed tomography (CBCT) scan will be taken per standard care.

Prior to surgery, pregnancy status will be confirmed verbally. An over-the-counter pregnancy test will be provided if pregnancy status is unknown or suspected (research). A negative result is required to continue being in the study.

Visit 5 - Implant placement:

Prior to surgery, pregnancy status will be confirmed verbally. An over-the-counter pregnancy test will be provided if pregnancy status is unknown or suspected (research). A negative result is required to continue being in the study.

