11.2. Continued Follow-up Discontinuation of Study Intervention

Describe efforts that will be made to continue follow-up of participants who discontinue the study intervention, but remain in the study for follow-up, especially for safety and efficacy study endpoints (if applicable). Reasonable efforts must be made to undertake protocol-specified safety follow-up procedures to capture adverse events (AE), serious adverse events (SAE), and unanticipated problems involving risks to subjects or others (UPIRSOs).

All patients that participate in the study, including those discontinued due to adverse reactions, will be followed until completion of the study or resolution of the adverse reaction (unless consent has been withdrawn).

12. Statistical Considerations

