12.3. Populations for Analyses

Clearly identify and describe the analysis datasets (e.g., which participants will be included in each).

All study participants who complete the study intervention will be included in the analysis for all outcome measures.

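### Section 10.2 exits randomized, grafted patients who miss a visit, although Visits 3 and 4 supply no endpoint: a small, avoidable post-randomization exclusion

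*Combined protocol and SAP*

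**What the plan says.** Section 10.2 requires attendance at every scheduled visit and then says "Failure to attend visits will result in exit from the study". It does not distinguish between visits, define a missed visit, or mention rescheduling.

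The visit outline in Section 5.3 shows what each visit contributes. At Visit 3, "At this visit a clinic exam will be performed to evaluate healing", and remaining sutures are removed. At Visit 4, "the patient will be seen for pre-implant evaluation, per standard care", with a CBCT scan if needed and a pregnancy check. The clinical endpoints in Section 3 are "Change in ridge width; Change in buccal ridge height; Change in lingual ridge height", measured at Visits 2 and 5. The histologic endpoints come from the core taken at Visit 5. On that core the protocol says that "collection of normally discarded bone core for analysis is a research procedure".

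Section 11.2 says "All patients that participate in the study, including those discontinued due to adverse reactions, will be followed until completion of the study", or until the adverse reaction resolves, unless consent is withdrawn. Section 12.3 says "All study participants who complete the study intervention will be included in the analysis for all outcome measures".

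**The concern.** A randomized comparison is best protected by keeping every randomized patient whose outcome can be measured. Section 10.2 removes some of them for a reason that does not prevent measurement. A patient who skips the healing check or the pre-implant evaluation, and then has the implant placed, is still in the chair at Visit 5 with a core that would otherwise be discarded. Because taking the core and the stent measurements for analysis is research rather than routine care, exit from the study probably means that they are not taken.

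What is at stake is selection. If patients who heal badly (or well) are more likely to miss a visit, and this happens more in one arm than in another, the completers in that arm no longer represent it. The plan creates this exclusion itself, so it can be avoided.

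**Working it through.** **Timing.** Section 5.3 places randomization at Visit 2 after extraction; Section 10.1 has the envelope drawn before the surgical appointment. On either account Visits 3 and 4 come later, so any exit for missing them is post-randomization.

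**What each visit supplies.**

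| Visit | Content | Section 3 endpoint |
|---|---|---|
| 2 | Extraction, graft, baseline stent measurements | Baseline for ridge width and height |
| 3 | Healing exam, suture removal | None |
| 4 | Pre-implant evaluation, pregnancy check | None |
| 5 | Pregnancy check, repeat stent measurements, core | All histologic endpoints; follow-up for ridge change |

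The pregnancy check at Visit 4 is repeated at Visit 5, so missing Visit 4 does not by itself block outcome collection.

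**The plan's own figure.** Section 12.2 inflates 16 per group for 20% attrition: 16 / (1 − 0.20) = 20, which reproduces. Enrollment is then set at 30 per group.

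**Power.** Inputs from Sections 12.2 and 12.4: difference 15 points, SD 15, two-sided 5%. The two-sample t-test (noncentral t, unadjusted) gives 96.8% power at 30 per arm. After 20% attrition, 30 × 0.80 = 24 per arm gives 92.4%. If a further 20% of those 24 were exited (assumed), 24 × 0.80 = 19.2, so 19 whole patients remain and power is 85.1%. Power is not the problem.

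**Bias, illustrative.** The documents give no missed-visit rate and no link between attendance and healing, so both are assumed. Let a patient be lost when a latent attendance variable, with correlation ρ to % vital bone, falls below its q-quantile z_q. The mean of those retained then shifts by

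shift = ρ × 15 × φ(z_q) / (1 − q).

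- q = 0.05, φ(z_q) = 0.1031: 0.3 × 15 × 0.1031 / 0.95 = 0.49; with ρ = 0.5, 0.81.
- q = 0.10, φ(z_q) = 0.1755: 0.3 × 15 × 0.1755 / 0.90 = 0.88; with ρ = 0.5, 1.46.
- q = 0.20, φ(z_q) = 0.2800: 0.3 × 15 × 0.2800 / 0.80 = 1.57; with ρ = 0.5, 2.62.

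Simulated rejection rates at nominal 5%, with no true difference, 30 randomized per arm and 200,000 runs (Monte Carlo SE about 0.05 percentage points):

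| Loss | t-test, ρ = 0.3 / 0.5 | Four-arm ANOVA, ρ = 0.3 / 0.5 |
|---|---|---|
| 5%, one arm only | 5.2% / 5.5% | 5.1% / 5.3% |
| 10%, one arm only | 5.5% / 6.5% | 5.3% / 6.1% |
| 20%, one arm only | 6.6% / 9.6% | 6.1% / 8.4% |
| 10% in both arms | 5.0% / 5.0% | not run |

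Equal and equally selective loss gives no bias in the difference. The 20% row attributes the whole planned attrition rate to this rule, in one arm only. It is an upper scenario, not an expectation.

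**The case against.** The strongest reply is that the rule may affect almost nobody. It costs an outcome only for a patient who never attends Visit 3 or 4 and still has the implant placed. The visit timings are approximate, and 10.2 does not forbid rescheduling. A patient who never attends the pre-implant evaluation may well not reach surgery. That would be ordinary loss to follow-up, within the 20% attrition of 12.2. Section 6.3 already excludes people who will not keep to the schedule, although only at entry. Section 5.3 says that the patient is blinded, which makes attendance that differs by arm less likely. It does not exclude it, since healing that differs by arm can itself affect attendance, and Section 10.1 limits blinding to the histomorphometry. The illustration is also severe: at 10% loss, ρ of 0.3 to 0.5 implies that lost patients average about 8 to 13 points below their arm's mean (ρ × 15 × 0.1755 / 0.10). Even so, error stays near nominal. All of this limits the size of the point. None of it gives a reason for the exclusion.

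Four stronger readings are tempting but not supported.

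- *That 10.2 flatly contradicts 11.2.* Section 11.2 is headed as follow-up after discontinuation of the intervention and refers to resolution of an adverse reaction. It can be read as continued study follow-up for everyone, or as safety follow-up that coexists with exit from research data collection. The two sections need reconciling; a contradiction is only one reading.
- *That 12.3 drops these patients.* Section 7 defines the intervention as ridge preservation, so a grafted patient has completed it and belongs in the analysis. The difficulty is that such a patient has no outcome to contribute if 10.2 prevents its collection.
- *That the protocol treats the interim visits as optional.* Section 5.3 does say "During the 18 to 20-week healing period, patients will be followed as needed per standard care to evaluate healing", but this can describe additional standard-care visits, because a visit-by-visit outline follows it.
- *That the differing Visit 3 windows cause exits.* Section 5.3 gives 1 to 3 weeks in one place and 3 weeks ± 1 week in another. These should be reconciled, but nothing ties the difference to exit.

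**Conclusion.** The point holds as a minor, low-severity improvement. As written, 10.2 discards randomized and grafted patients for missing visits that supply no endpoint, when their core and final ridge measurements could still be obtained. That the core would not be taken after exit is an inference from its status as a research procedure; the protocol does not say so directly.

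The number affected is unstated and probably small, and power is ample. Bias needs loss that is both related to healing and different between arms. Under the assumed 5% to 10% loss in one arm and correlation 0.3 to 0.5, the shift is about 0.5 to 1.5 points against a 15-point target difference, with rejection of 5.2% to 6.5% for the t-test and 5.1% to 6.1% for the ANOVA. A reader should not infer that the trial's conclusions are at material risk; the case for change is that the exclusion serves no stated analytic purpose and costs almost nothing to remove.

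**What to change.** - **Section 10.2:** replace automatic exit with a rule that a missed Visit 3 or Visit 4 is recorded as a protocol deviation, that the patient stays in data collection, and that the Visit 5 measurements and core are obtained if implant surgery goes ahead under the existing procedures. Leave the pregnancy and consent-withdrawal rules unchanged.
- **Section 11.2:** state whether it means continued study follow-up or safety follow-up after discontinuation, and align it with 10.2.
- **Section 12.3:** analyse histology in all randomized and grafted patients with an evaluable core, and ridge dimensions in all randomized and grafted patients with Visit 2 and Visit 5 measurements. Use the allocated arm, whatever the attendance at Visits 3 and 4. Both remain complete-case sets, so report patients without outcomes by arm and reason.

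The cost is a few more recorded deviations and one extra table. No visits, staff or procedures are added.
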